2.0 Rationale and Specific Aims

Biologically informed precision treatment could benefit smokers in several ways. Biological tailoring may increase the salience of messaging about smoking-related disease and advice to quit. This in turn could reduce the optimistic bias, a tendency to underestimate one's own health risk, which hinders cessation efforts⁹, thereby increasing motivation to quit. Data has demonstrated that the nicotine metabolite ratio (NMR), a biomarker reflecting CYP2A6 activity, can inform choice of smoking cessation pharmacotherapy, such that "fast/normal" metabolizers are twice as likely to quit smoking on varenicline compared to "slow" metabolizers⁶. Additionally, smokers who are presented results from a commercially available, gene-based lung cancer risk assessment, Respiragene, are more likely to undergo lung cancer screening¹⁰⁻¹³. Respiragene recipients were also more likely to use nicotine replacement therapy (NRT) and quit smoking^{5,14-16}. Though promising tools to help engage smokers in cessation treatment, these individual, biologically informed feedback interventions have not yet been studied in community smokers in the US.

Our overarching aim is to leverage the SCCS and the U54 Community Outreach Core Community Advisory Board (CAB) to guide the development of two precision care (PC) interventions for smoking cessation: PC-NMR and PC-Respiragene. Both will be tailored to attitudes and beliefs of low socioeconomic status (SES) community smokers in the southeastern US, where tobacco use prevalence is one of the highest in the country. PC is rooted in the PRIME Model of behavior change¹⁷⁻¹⁹, which reflects a multi-faceted view of motivation for tobacco cessation. We will assess feasibility of PC in SCCS participants who smoke and conduct a 3-arm randomized controlled trial (RCT) to determine preliminary estimates of PC interventions vs. standard guideline-based care (GBC) on engagement^{4,20}, smoking cessation, and likelihood of undergoing recommended lung cancer screening if eligible²¹. Our hypothesis is that, compared to GBC, PC participants will exhibit higher smoking cessation and lung cancer screening rates. These effects will be explained by lower optimistic bias, higher self-efficacy and motivation to quit, and use of proven quit aids (medication, behavior therapy via state quit line).

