All participants assigned to guideline based care (GBC) will be referred to the state quitline and will receive a smoking cessation intervention through the National Cancer Institute's (NCI) "Clearing the Air" program. Additionally, as part of clinical care, the primary care provider (PCP) will document guideline-based treatment recommendations and provide participants with prescriptions sufficient for a 3-month course of pharmacotherapy chosen at the clinical discretion of the provider. Written and verbal instructions will be provided to participants given medication to contact their primary provider and the research study staff (during regular business hours) to address any questions about medication. Participants will be instructed to call 911 if they believe they are having a medical emergency. GBC participants will also receive Respiragene and nicotine metabolite ratio (NMR) testing on their SCCS stored blood sample and will be informed of these results at the end of the study.

Respiragene Precision Care Group (PC-Respiragene)

All participants assigned to Respiragene precision care will receive guideline-based care, including a referral to the state quitline, as described above. Additionally, the PCP will have clinical decision support regarding the interpretation of the Respiragene test. Study staff will discuss results of the Respiragene test with the participant and the PCP will provide participants with prescriptions sufficient for a 3-month course of pharmacotherapy chosen at the clinical discretion of the provider based on guidelines relevant to differential health risks.

NMR Precision Care Group (PC-NMR)

All participants assigned to NMR precision care will receive guideline-based care, including a referral to the state quitline, as described above. Additionally, the PCP will have clinical decision support regarding the interpretation of NMR from the study team. Using the NMR data, the PCP will discuss

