results with the participant and provide participants with prescriptions sufficient for a 3-month course of pharmacotherapy based on NMR results (NRT for “slow” metabolizers and non-nicotine smoking cessation medication (varenicline) for “fast/normal” metabolizers). Participants who do not wish to receive varenicline, may have the option of a higher nicotine patch dose that has been studied previously. In this previous study, there were no significant differences between treatment arms in the frequency of severe side effects and serious adverse events or blood pressure during treatment ($p > .10$).²²

Participants may receive prescriptions through their own pharmacies or through a mail order pharmacy.

Check-in phone calls

Study staff will call participants at approximately 2 weeks after the study results call, and again approximately 1- 2 months following the results call, to encourage medication adherence and assess self-reported tolerance. If additional communication is needed, a tobacco counselor can be available for extra calls.

Table 1: RCT Data Collection Table for Aim 3					
Follow up Assessments	B L	1 mo f/u	Informal Check-in (2)	3 mo f/u	6 mo f/u
Smoking status	X	X		X	X
Cigarettes per day	X	X		X	X
Health risk perceptions	X	X		X	X
Lung cancer screening	X	X		X	X
Notify of PC results*		X			X
Calls to support med		X	X	X	

Outcome assessment

Subject outcomes will be assessed via phone calls at approximately 1, 3, and 6 months, as shown in Table 1. At follow up, an RA who is separate from intervention staff will complete interviews assessing smoking behavior, medication use and self-reported side effects, patient health risk perceptions and attitudes toward the PC interventions, and whether the patient received a lung cancer screening. Participants reporting abstinence at six months will be mailed a standard salivary cotinine kit for biochemical validation of smoking abstinence, defined as ≤ 10 ng/ml.

adherence, tolerance					
CO-validated abstinence					X
*Participants in PC arms (Respiragene, NMR) notified of results; GBC participants are contacted to match for time					

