7.0 Risks

Nicotine Metabolite Ratio (NMR), Respiragene, & Salivary Cotinine Test: There are no known serious adverse effects from these tests.

Breach of confidentiality: All efforts, within reason, will be made to keep personal information in the research records confidential. Total confidentiality cannot be guaranteed. To prevent a breach of confidentiality, participant data will be collected using password protected and encrypted computers, and electronic participant tracking spreadsheets stored on a secure server. All paper records will be locked in secure areas and accessible to study staff only. To prevent the loss of data, all electronic information is password protected on anti-virus software enabled computer systems. Only study staff will have access to the study data on Shared File Areas. Participants will be identified on study forms and in the database by a participant number. Participant names and contact information will be stored in a separate file.

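### Six-month abstinence is validated by salivary cotinine alone, with no stated handling of abstainers still using non-smoked nicotine, and Table 1 labels the same outcome differently (minor)

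*Combined protocol and SAP*

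**What the plan says.** Section 6.0, Outcome assessment: participants who report abstinence at six months "will be mailed a standard salivary cotinine kit for biochemical validation of smoking abstinence, defined as ≤ 10 ng/ml". This is the only criterion. There is no exception, alternative test or separate category for people using nicotine products.

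Section 6.0, Table 1 marks the six-month item as "CO-validated abstinence". CO is not defined, and no carbon monoxide procedure or cutoff is given. The test list in Section 7.0 reads "Respiragene, & Salivary Cotinine Test" after the NMR entry and names no carbon monoxide test.

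NRT is a study treatment, and Section 6.0 gives each arm its own route to it:
- PC-NMR: "prescriptions sufficient for a 3-month course of pharmacotherapy based on NMR results", with NRT for one metabolizer group and varenicline for the other. Those not wanting varenicline "may have the option of a higher nicotine patch dose".
- PC-Respiragene: pharmacotherapy "chosen at the clinical discretion of the provider based on guidelines relevant to differential health risks".
- GBC: the provider's own choice.

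All three arms receive prescriptions for a 3-month course. Section 7.0 adds that some NRT is available without prescription.

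The follow-up calls include "interviews assessing smoking behavior, medication use and self-reported side effects". Nothing says whether this extends to non-prescribed nicotine.

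Section 10.0 lists biochemically validated cessation at 6 months among the Aim 3 estimates and promises a look at differences between groups. It also says that feasibility is primary and that the trial is not powered for cessation.

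**The concern.** Cotinine is a metabolite of nicotine, whether the nicotine comes from a cigarette, a patch or gum. This is general pharmacology; the documents do not state it, and no outside figure is needed. Under the cotinine rule alone, a person who has stopped smoking but still uses a nicotine product looks the same as a person who smokes. In a trial that supplies NRT, the validated rate can therefore understate smoking cessation. If such use is unequal across arms, the arm contrasts can move as well.

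Two gaps leave this open. The plan does not say how an unvalidated self-report is analysed, and it names no second estimate that would show how many people are involved. A second estimate chosen after the data are seen would be post hoc.

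The Table 1 label adds to the uncertainty. A carbon monoxide test and a cotinine test would classify nicotine product users differently, so the label bears on who counts as abstinent.

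At stake are the preliminary cessation estimates that the pilot is meant to hand on to the design of a later trial. No powered comparison is at stake.

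**Working it through.** The plan states no quit rate, NRT share or six-month nicotine use, so it has no figure to reproduce. The size below is illustrative.

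**Inputs from the documents.** Up to 100 participants randomised 1:1:1 (Section 2.0), so 100/3 = about 33 per arm. Prescriptions cover 3 months (Section 6.0). Validation is at month 6 (Section 6.0, Table 1).

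**Assumed inputs.** *p* is the true smoking-abstinence rate, taken as 10%, 20% or 30%. *u* is the share of true abstainers above the cutoff because of non-smoked nicotine, taken as 0% to 25%. Self-report is assumed accurate and every kit is assumed to come back.

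**Timing.** Table 1 places the results contact at the 1-month follow-up. A 3-month course started then ends at about 1 + 3 = month 4. Nicotine use at month 6 therefore needs a late start, an extension or a non-prescribed product. This points to a small *u*, but not to zero.

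**Understatement of one arm's rate, unvalidated cases analysed as non-abstinent.** Validated rate = *p*(1 − *u*), so the loss is *pu*. At the upper end, *u* = 25%:
- *p* = 10%: 0.10 × 0.25 = 2.5 points; 0.025 × 33 = 0.8 participants.
- *p* = 20%: 0.20 × 0.25 = 5 points; 0.05 × 33 = 1.65 participants.
- *p* = 30%: 0.30 × 0.25 = 7.5 points; 0.075 × 33 = 2.5 participants.

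A milder case: half of abstainers used NRT and 10% to 20% of those still do at month 6. Then *u* = 0.5 × 0.10 = 5% to 0.5 × 0.20 = 10%. At *p* = 20% the loss is 1 to 2 points, or 0.3 to 0.7 of 33 participants.

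**The same, unvalidated cases analysed as missing and left out.** Rate = *p*(1 − *u*)/(1 − *pu*). At *u* = 25%:
- *p* = 10%: 0.075/0.975 = 7.7%, a loss of 2.3 points.
- *p* = 20%: 0.15/0.95 = 15.8%, a loss of 4.2 points.
- *p* = 30%: 0.225/0.925 = 24.3%, a loss of 5.7 points.

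The unstated analysis rule changes the size somewhat, but not the order of magnitude.

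**Arm differences.** With equal true abstinence and unvalidated cases analysed as non-abstinent, the shift in a contrast is *p* times the difference in *u* between the two arms. It is zero if *u* is equal and can take either sign if it is not. With *u* confined to 0% to 25%, it cannot exceed 2.5, 5 or 7.5 points at the three values of *p*.

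**Sampling error for comparison.** 95% half-width of a difference = 1.96 × √(2*p*(1 − *p*)/33):
- *p* = 10%: 1.96 × √(0.18/33) = 14.5 points.
- *p* = 20%: 1.96 × √(0.32/33) = 19.3 points.
- *p* = 30%: 1.96 × √(0.42/33) = 22.1 points.

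**Label.** The Outcome assessment text and Section 7.0 both name salivary cotinine. Only the Table 1 row says CO. Follow-up is by telephone with a mailed kit, which fits cotinine.

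**The case against.** The strongest reply is that this hardly matters. Prescribed courses should be over by month 6, cessation is exploratory, and the plausible loss is a fraction of a participant to a few participants per arm. Much of the data is also already planned: smoking status is collected at six months, the interview covers medication use, and Section 10.0 promises descriptive and exploratory analyses. A self-reported rate could be tabulated without changing the protocol.

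Most of this stands and sets the grade at minor. What remains is that the plan does not commit to the tabulation, does not say that non-prescribed nicotine is asked about, and does not define the analysis of unvalidated cases.

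A reader might infer three stronger claims that the documents do not support:
- **That the contrasts are biased in a known direction.** Section 2.0 says "Respiragene recipients were also more likely to use nicotine replacement therapy (NRT) and quit smoking", which might suggest more unvalidated abstainers in PC-Respiragene. But that concerns uptake in earlier studies, not use at month 6. Here every participant must be willing to accept a prescription, and all arms receive one.
- **That the distortion is large.** Spurious gaps of 2 to 12 points arise only if *u* differs between arms by 20 to 40 points. Nothing in the documents supports differences of that size.
- **That unvalidated abstainers are counted as smokers.** The plan does not say so; they might equally be treated as missing.

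**Conclusion.** The point holds as a minor one. As written, the rule does not validate a self-reported abstainer who exceeds the cutoff through non-smoked nicotine. The analysis of such a case is unspecified, and no parallel estimate is named. NRT is reached by a different route in each arm and is also available without prescription, so the number affected may differ by arm, in an unknown direction.

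The effect is probably small. Over the assumed range the loss in an arm's rate runs from 0 to 7.5 points, and 1 to 2 points in the milder case. All of this lies well inside the half-width of about 14 to 22 points for an arm difference. Every size rests on assumed abstinence and assumed nicotine use; no bias has been demonstrated.

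The label mismatch is a definite inconsistency. Cotinine appears to be what is meant, but only the sponsor can confirm that.

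**What to change.** 1. Reconcile the Table 1 label with the Outcome assessment text. Cotinine-validated appears intended; the sponsor should confirm.
2. Extend the medication-use item in the existing six-month interview to current use of any nicotine product, including non-prescribed ones.
3. Keep the cotinine-validated rate as the main estimate, and state whether unvalidated cases are analysed as smoking or as missing.
4. Prespecify a second estimate for all three arms in which self-reported abstainers with current non-smoked nicotine use are not classified as non-abstinent on cotinine alone. Report the number affected per arm.

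The cost is one table label, one longer interview item, one sentence on the analysis rule and one extra tabulation by arm. No treatment changes and no new contact is needed. The downside is that the second estimate relies on unverified self-report for nicotine users, so it must be read beside the main estimate and not replace it. If no one is affected, the tabulation will show that.

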7.0 Risks

Nicotine Metabolite Ratio (NMR), Respiragene, & Salivary Cotinine Test: There are no known serious adverse effects from these tests.

Breach of confidentiality: All efforts, within reason, will be made to keep personal information in the research records confidential. Total confidentiality cannot be guaranteed. To prevent a breach of confidentiality, participant data will be collected using password protected and encrypted computers, and electronic participant tracking spreadsheets stored on a secure server. All paper records will be locked in secure areas and accessible to study staff only. To prevent the loss of data, all electronic information is password protected on anti-virus software enabled computer systems. Only study staff will have access to the study data on Shared File Areas. Participants will be identified on study forms and in the database by a participant number. Participant names and contact information will be stored in a separate file.

Adverse drugs reactions: Participants in this study may receive one of two FDA-approved smoking cessation therapies (NRT or varenicline) and will have the potential to experience drug-related side effects. Nicotine replacement therapy is generally very safe and several preparations of it have been sold over the counter for decades). However, possible side effects include, but are not limited to, skin irritation or itching (patch), dizziness, headache, nausea, mouth/throat irritation (inhaler/nasal spray), and rapid heartbeat. Common side effects of varenicline include nausea, sleep disturbance and vivid dreams, gastrointestinal symptoms, and vomiting. Very rarely, patients, particularly those with unstable psychiatric conditions, may experience symptoms such as behavioral changes, agitation, depressed mood, and suicidal behavior during varenicline treatment. In a large FDA-mandated trial (EAGLES, Lancet 2016) all three of these medications were found to be safe and effective in patients with and without pre-existing psychiatric conditions.²³ To protect against risk from pharmacotherapy usage, this study will only use FDA-approved smoking cessation medications and tobacco treatment providers will screen patients to identify contraindications to NRT or varenicline. Written and verbal instructions will be provided to patients given medication to contact their primary physician and the research PI, [name], in case of adverse effects of a medication. Additionally, study staff will call participants during active treatment to monitor for medication side effects. Ultimately, the PI ([name]) will review any serious adverse events and report them appropriately to the IRB.

8.0 Reporting of Adverse Events or Unanticipated Problems Involving Risk to Participants or Others

Any serious adverse events will be reported to the IRB and NIH according to appropriate policies and procedures. Serious adverse events are defined as untoward or undesirable medical events, related to study procedures, that 1) are of at least moderate severity as reported by participants at follow-up; 2) require hospitalization or ER visit; 3) are life-threatening or cause death or permanent impairment/disability; or 4) require intervention to prevent death or permanent impairment/disability.

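### Section 8.0 makes study-relatedness a condition of every SAE and lets participant-rated moderate severity suffice, while leaving open whether the cessation medication is a study procedure

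*Combined protocol and SAP*

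**What the plan says.** The SAE definition is one sentence in Section 8.0. It opens with the relatedness condition and the severity criterion, limiting SAEs to events "related to study procedures, that 1) are of at least moderate severity as reported by participants at follow-up". Criterion 2 is a hospital admission or emergency room visit. The list ends: "3) are life-threatening or cause death or permanent impairment/disability; or 4) require intervention to prevent death or permanent impairment/disability". On reporting, the section says: "Any serious adverse events will be reported to the IRB and NIH according to appropriate policies and procedures". It gives no severity scale, attribution procedure, definition of a non-serious adverse event, or rule for deaths and admissions judged unrelated. Its title also covers unanticipated problems, but the text has no rule for them.

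The cessation medication is described in several ways:

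- Section 6.0, Guideline Based Care Group: "as part of clinical care, the primary care provider (PCP) will document guideline-based treatment recommendations" and prescribes at the provider's discretion.
- Section 6.0, NMR Precision Care Group: the provider prescribes a "3-month course of pharmacotherapy based on NMR results". The NMR measurement paragraph likewise has the test result determine the drug.
- Section 7.0 lists drug reactions among the risks of taking part, without distinguishing arms.
- Section 10.0, Aim 3 primary analysis, counts use of the medication as an engagement measure and describes it as provided by the study.

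**The concern.** Seriousness, severity and relatedness are three separate attributes of an event. Seriousness concerns outcome, severity concerns intensity, and relatedness is a judgement about cause. Section 8.0 merges them into one definition, so the SAE count cannot be read as a count of serious outcomes. It leaves out serious outcomes that someone has judged unrelated, and it takes in symptoms with no serious outcome.

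The relatedness condition is also undefined where it matters most. The drugs are the main source of medical risk that the plan names, and a reader cannot tell whether a drug effect counts as related to study procedures. At stake are the reliability of what goes to the IRB and NIH, and the value of any SAE tabulation that this pilot passes on to a later trial.

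**Working it through.** **Step 1: the logic of the definition.** The documents give no figure to reproduce. Read literally, Section 8.0 says:

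SAE = (related to study procedures) AND (criterion 1 OR 2 OR 3 OR 4)

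| Event | Related? | Criterion met | SAE under Section 8.0? |
|---|---|---|---|
| Death | judged unrelated | 3 | No |
| Hospital admission | judged unrelated | 2 | No |
| Moderate nausea, no other feature | judged related | 1 | Yes |
| Moderate nausea, no other feature | judged unrelated | 1 | No |

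The first three rows are the problem: two serious outcomes are out and one non-serious symptom is in.

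**Step 2: the medication under each reading.**

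- *The medication is a study procedure* (Section 10.0 and the Section 7.0 risk list point this way). Moderate drug effects then become SAEs. Section 7.0 names the likely ones: "Common side effects of varenicline include nausea, sleep disturbance and vivid dreams, gastrointestinal symptoms, and vomiting".
- *The medication is ordinary clinical care* (the Guideline Based Care text points this way). A drug-caused admission then falls outside the definition. Section 7.0 knows of no serious adverse effects from the NMR, Respiragene and cotinine tests, so few medical events would remain to count.
- *It is decided case by case.* The same drug event could be classified differently from one participant or arm to another. The principal investigator reviews SAEs, and no blinded or independent attribution is described.

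**Step 3: scale, on assumed rates only.** Section 2.0 gives up to 100 participants randomised 1:1:1, so 100 / 3 ≈ 33 per arm at full enrolment. The event rates below are assumptions, not document figures.

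- Suppose 10% to 30% of an arm has a moderate drug effect, with everyone taking a drug. If all are judged related, criterion 1 alone yields 33 × 0.10 = 3.3 to 33 × 0.30 = 9.9 SAEs in that arm. If a quarter are judged related, it yields 3.3 × 0.25 = 0.8 to 9.9 × 0.25 = 2.5. If none are, it yields 0.
- Suppose 5% to 10% of 100 participants have an unrelated admission. That is 100 × 0.05 = 5 to 100 × 0.10 = 10 events, all counted as 0 SAEs.

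The first calculation shows only that the count depends heavily on an attribution rule that the plan does not state.

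**The case against.** **The definition governs reporting, not data collection.** Under Outcome assessment in Section 6.0, a research assistant separate from the intervention staff asks all arms about side effects at about 1, 3 and 6 months, and there are two check-in calls on tolerance. This stands against a reader inferring that relatedness is settled before anything is recorded: moderate drug effects are collected whether or not they are SAEs. It does not answer the point on unrelated admissions and deaths. The listed interview topics and Table 1 include no item for them, although the follow-up form itself is not shown.

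**Reporting follows IRB and NIH policies, which may ask for more.** That is possible and cannot be checked from the documents. But the phrase governs how SAEs are reported. It does not change which events the protocol calls SAEs.

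**Counting moderate related events is merely cautious.** This is fair for that criterion taken alone. It does not offset the omission of unrelated serious outcomes.

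**Arms are treated alike.** Both precision-care arms also receive guideline-based care, a primary care provider prescribes in every arm, Section 10.0 describes the drug as study-provided without regard to arm, and contact is matched for time. A uniform reading is therefore available. A reader might infer that the rule makes a between-arm safety comparison unfair, but the documents do not support that. Inconsistent attribution is a possibility that they leave open, not something they show, and Section 10.0 plans no between-arm safety analysis.

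**Conclusion.** The concern holds as a defect in a stated rule. Followed exactly, Section 8.0 excludes deaths, life-threatening events and admissions judged unrelated, and includes non-serious moderate symptoms judged related. No other section repairs this. That conclusion rests only on the wording and needs no assumed rate.

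The unclear status of the medication adds to it: whether drug-caused events qualify cannot be determined from the text, so classification could be inconsistent.

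The title of Section 8.0 and its first criterion might suggest that every moderate event is an SAE. That is too strong, because only those judged related qualify. The counts of 0 to 9.9 per arm and 5 to 10 overall are illustrations on assumed rates at full enrolment and should not be cited as expected numbers. The consequence is confined to SAE reporting and any tabulation. The primary feasibility outcome and the cessation estimates are unaffected. The change should be made, but the trial's main conclusions do not depend on it.

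**What to change.** 1. In Section 8.0, define SAEs by the existing outcome criteria 2 to 4, regardless of cause and in all arms.
2. Take moderate severity out of the SAE definition, and record severity as its own field for every adverse event, on a stated scale.
3. Record relatedness as a separate field, with the study test, the disclosure of results and the cessation medication as distinct possible causes.
4. Reconcile Sections 6.0, 7.0, 8.0 and 10.0 on whether the medication is a study procedure, and use one description throughout.
5. Tabulate SAEs descriptively by arm, with no formal test.

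The cost is more than rewording. The follow-up interviews need a question on admissions or emergency visits from any cause, someone must make and record the attribution, and unrelated events must be logged. In return, moderate symptoms with no serious outcome no longer need SAE reports. None of this changes a dose, a treatment rule or the design of the trial.
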